2. TRIAL OBJECTIVES AND HYPOTHESIS

2.1 Primary Objective

- To assess the safety and tolerability of 3 single ascending dose (SAD) levels and 3 MAD levels of DYN101.

2.2 Secondary Objectives

- To assess the PK of SAD and MAD of DYN101.
- To explore target engagement in muscle of DYN101.

2.3 Exploratory Objectives

- To investigate the effect of DYN101 treatment on the clinical assessments in various affected domains (respiratory, muscle strength and function, dysphagia).
- To explore the impact of CNM and its treatment on symptoms, functioning, and health-related QoL.
- To assess the presence of anti-drug antibodies (ADA) against DYN101 by collecting blood samples.
- To assess the metabolic profile of DYN101 by collecting blood and urine samples.
- To contribute to the global understanding of CNM and its treatment by collecting blood and muscle samples for further exploratory biomarker/genetic research.

2.4 Hypothesis

As this trial is designed to provide descriptive information regarding safety and tolerability, no formal statistical hypothesis testing is planned.

3. TRIAL DESIGN

3.1 Overall Trial Design

[figure not shown]
3.1.1 Overview of Trial Periods

This is a first-in-human, Phase 1/2, open-label, multi-center trial to evaluate the safety, tolerability, PK, PD and preliminary efficacy of DYN101 after SAD and MAD in subjects ≥ 16 years of age* with CNMs caused by mutations in *DNM2* or *MTM1* (*for Germany, the subject must be ≥ 18 years of age in accordance with local and national regulations).

Sufficient subjects will be screened in order to ascertain that approximately 18 subjects will be dosed and finish the trial. Subjects may be recruited from an ongoing NHS (Nat-His-CNM Trial Protocol, 2017).

There will be stand-by subjects for replacement of subjects who discontinue the trial early, if needed. Stand-by subjects will perform run-in visits until the last MAD subject has completed Week 13, unless needed for replacement.

The trial will consist of a pre-screening consent, a screening period, a run-in period (if applicable), a SAD part with 4 weeks of follow-up after IMP administration and a washout period of at least 12 weeks (followed by follow-up phone calls until the MAD part starts), a MAD part of 12 weeks, and a MAD extension part of 12 weeks. All subjects will participate in the SAD, MAD and MAD extension parts, unless they withdraw. End of Treatment (EoT) assessments will be performed after 24 weeks of MAD treatment have been completed, i.e. at the Week 25 visit. Subjects will return to the clinic 3 months after the last IMP administration, to follow-up on the subject's status including abnormal laboratory results, AEs, and concomitant medications. The trial design is presented in Figure 1.

Abbreviations: BL: baseline, EoT: End of Treatment, FU: follow-up, MAD: multiple ascending dose, SAD: single ascending dose, SCR: screening, W: week

* All subjects will remain on treatment with weekly IMP administrations and bi-weekly (every 2 weeks) assessments until the last MAD3 subject has completed the MAD Week 25 visit. The data generated from these bi-weekly assessments will not be part of the statistical analysis for this trial (see Section 9.1).

Figure 1: Trial Design: Trial Periods

Subjects will give a 'pre-screening' consent to be entered as 'pre-screened' in the Interactive Response Technology (IRT) system. The pre-screening consent process can be managed remotely (please refer to the Site Operations Manual for more details). Subsequently, subjects will sign the main informed consent form (ICF) and screening will be performed to assess eligibility. Subjects who are participating in the NHS and have at least 2 data time points available from the NHS to assess their pre-trial condition do not require a mandatory run-in visit.

Subject screening should be performed within 6 weeks before the baseline visit. There should be a minimum of 3 data time points to assess their pre-trial condition. The screening visit can be the third data time point.

Subjects who have not participated in the NHS or who do not have at least 2 data time points from the NHS will have a mandatory run-in period before continuing to the baseline visit. At least 1 run-in visit needs to be performed for these subjects in order to obtain 3 data time points to assess their pre-trial condition; screening can be the first data time point, baseline can be the third data time point. There should be a minimum of 28 days between screening and the first run-in visit. Run-in visits may be repeated until the assigned cohort can start (see Section 6.1.2). The run-in period is optional for stand-by subjects who participated in the NHS and have at least 3 data time points.

At baseline, subjects will be enrolled into the trial (if all in- and exclusion criteria are still met) until recruitment in the last cohort is reached, including replacement subject(s) who were amongst the stand-by subjects. Stand-by subjects will perform run-in visits until the last MAD subject has completed Week 13, unless needed for replacement.

In the SAD part, subjects will receive a single dose of IMP at Day 1. In the MAD part, subjects may receive the same or a different dose as in the SAD part, with weekly administrations of IMP for a period of 12 weeks, followed by a MAD extension part with an additional 12 weeks of treatment (weekly administrations). After Week 24, all subjects will remain on treatment with weekly IMP administrations and bi-weekly (every 2 weeks) assessments until the last MAD3 subject has completed the MAD Week 25 visit. In order to avoid any overlaps, a given MAD cohort may not start before its corresponding SAD cohort is finished.

Subjects will receive DYN101 in a low (1.5 mg/kg), middle (4.5 mg/kg), or high (up to 9 mg/kg) dose level in Cohorts 1, 2 and 3, respectively. In the MAD part, subjects may receive a different dose than what they received in the SAD part. In each cohort, there will be up to 6 subjects with a mutation in *DNM2* (sub-cohort a) and up to 3 subjects with a mutation in *MTMI* (sub-cohort b).

Cohorts will be enrolled in a sequential, staggered approach, with an interval of at least 7 days between dose administration of the first and the next subject in a cohort, irrespective of their sub-cohort. The first subject (i.e. the sentinel subject) in each cohort will be ≥ 18 years of age. The 48-hour safety data from the first subject in a cohort will be reviewed by the medical monitor before the next subject can be dosed. In addition, any SAE data from the first subject received up until the moment of treatment of the second subject will be taken into account.

Pausing/stopping rules will be applied in this trial (see Section 7.11).

[figure not shown]
An IDMC will be established to monitor the safety data on a regular basis to ensure the continuing safety of the enrolled subjects. The IDMC may meet at any time based on emerging safety and tolerability data. At a minimum, the IDMC must meet after all subjects of a cohort have been dosed to advise to continue each *MTMI* and/or *DNM2* sub-cohort to the next dose level/or discontinue the *MTMI* and/or *DNM2* sub-cohort of the trial. Escalation of each *MTMI* and/or *DNM2* sub-cohort to the next increased dose level will not take place until the IDMC has reviewed the data of the previous sub-cohort (including subjects who have discontinued the trial). The data reviewed by the IDMC for dose escalation decisions will be as clean as possible prior to their review. The IDMC can recommend adjusting dose levels or stopping the dose escalation scheme for each *MTMI* and/or *DNM2* sub-cohort and/or individual subject based on the totality of available data (safety and tolerability data and/or level of target engagement). At each IDMC review, different decisions for the sub-cohorts (*DNM2* vs *MTMI*) can be made based on the

emerging data. If needed, the IDMC review can be split over separate meetings for the sub-cohorts, although the available data from the other sub-cohort will also be taken into account at each meeting.

The IDMC will convene at least 4 times:

- The trial will start with the enrollment of approximately 6 subjects in Cohort SAD1.
- Cohort SAD2 can start after a favorable IDMC review of the 2-week safety and PK data of SAD1 (IDMC1).
- Cohorts SAD3 and MAD1 can start after a favorable IDMC review of the 2-week safety and PK data of SAD2 (IDMC2).
- Cohort MAD2 can start after a favorable IDMC review of the 2-week safety and PK data of SAD3, if available, as well as the 6-week safety and PK data of MAD1 (IDMC3).
- Cohort MAD3 can start after a favorable review of the 12-week safety and PK data of MAD1 and MAD2 as well as the MAD1 and MAD2 12-week PK and muscle biopsy data (IDMC4). In this meeting the IDMC will also recommend a starting dose for the pediatric DYN101-C102 study.

Details of the IDMC review will be described in the IDMC charter (see Section 9.12).

IDMC1: review of 2-week safety and PK data of SAD1; IDMC2: review of 2-week safety and PK data of SAD2; IDMC3: review of 2-week safety and PK data of SAD3, if available, and 6-week safety and PK data of MAD1; IDMC4: review of 12-week safety and PK data of MAD1 and MAD2, and 12-week PK and muscle biopsy data of MAD1 and MAD2.

Figure 2: Trial Cohorts and IDMC Reviews

Safety and tolerability will be evaluated throughout the trial from signing of the main ICF onwards until the last trial visit (i.e. EoT follow-up visit 3 months after the last IMP

administration). Safety evaluations will include monitoring of SAEs/AEs, clinical laboratory tests, ECGs, vital signs, and physical examinations at specified time points.

All enrolled subjects will undergo blood sampling for PK evaluations at specified time points. In addition, blood and/or urine samples will be collected for analysis of ADA and metabolic profiling.

PD/exploratory efficacy parameters including respiratory function, muscle strength and function, and dysphagia will be assessed, and a muscle biopsy will be taken at specified time points.

For subjects who provided a separate informed consent, blood samples will be collected for further exploratory research on blood biomarkers (including DNA). Participation in this part of the trial is optional and does not impact the subject's eligibility for participation in the trial. Subjects may continue to participate in the trial if they refuse to provide a sample or if they withdraw their samples.

The impact of CNM and its treatment (safety and efficacy) on QoL and health outcomes will be evaluated at specified time points, using questionnaires.

For an overview of the safety, PK and PD/exploratory efficacy assessments, please refer to the [TRIAL SCHEDULES](#).

An interim analysis will be performed when all subjects in Cohorts 1 and 2 have completed 12 weeks of MAD treatment or discontinued earlier, or if the sponsor deems a risk/benefit analysis necessary at any time point. The primary analysis will be performed when all subjects in all cohorts have completed 12 weeks of MAD treatment or discontinued earlier. The final analysis will be performed when all subjects have completed 24 weeks of MAD treatment (12 weeks in the MAD part + 12 weeks in the MAD extension part; Week 25 visit) or discontinued earlier.

The duration of participation in the trial for an individual subject in any cohort, from screening (excluding run-in period) to the last trial visit, will be at least 60 weeks.

The end of the trial is defined as the last visit of the last subject.

Further details will be described in the site manuals (e.g. Laboratory Manual, Site Operations Manual, Pharmacy Manual).

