Time Window	±1d	±1d	±1d	±1d	±1d	±3d	±3d	±3d	±3d	±3d	±3d	±3d	±3d	±3d	±3d
Administrative															
Concomitant medications	✓	✓	✓	✓	✓	✓	✓	✓	✓	✓	✓	✓	✓	✓	✓
IMP administration (IV) ^{d)}	✓			✓		✓	✓	✓	✓	✓	✓	✓	✓	✓	✓
Safety Assessments															
Physical examination ^{e)}	✓									✓					
Triplicate 12-lead ECG	✓									✓					
Vital signs (pulse rate, BP, RR, temperature, pulse oximetry) ^{g)}	✓		✓	✓		✓	✓	✓	✓	✓	✓	✓	✓	✓	✓
Liver ultrasound including hepatic elastography	(✓) ^{g) h)}														
Platelet count ^{f) g) i)}	✓		✓ ^{k)}	✓		✓	✓	✓	✓	✓	✓	✓	✓	✓	✓
Clinical laboratory assessments ^{f) g) j)}	✓ ^{l)}	✓	✓	✓	✓	✓	✓	✓	✓	✓	✓	✓	✓	✓	✓
Cardiac troponin ^{f) g) k)}	✓					✓		✓				✓			
Complement assessments ^{f) g) k)}	✓					✓		✓				✓			
Coagulation assessments ^{f) g) m)}	✓		✓	✓		✓	✓	✓	✓	✓	✓	✓	✓	✓	✓
Erythrocyte sedimentation rate ^{f) g) m)}	✓		✓	✓		✓	✓	✓	✓	✓	✓	✓	✓	✓	✓
Urinalysis (dipstick) ^{g)}	✓					✓		✓				✓			
Urine pregnancy test ^{g) n)}	✓							✓				✓			
Collect AEs/SAEs	✓	✓	✓	✓	✓	✓	✓	✓	✓	✓	✓	✓	✓	✓	✓

MAD PART															
Trial Period	Multiple Dose Treatment Period ^{a) b)}														
Time Point: Day (D)/Week (W)	MAD W1			MAD W2		MAD W3	MAD W4	MAD W5	MAD W6	MAD W7	MAD W8	MAD W9	MAD W10	MAD W11	MAD W12
	D1 ^{c)}	D2	D4	D8	D11										
Time Window	±1d	±1d	±1d	±1d	±1d	±3d	±3d	±3d	±3d	±3d	±3d	±3d	±3d	±3d	±3d
PK Assessments															
Blood sample for PK	✓ ^{o)}	✓		✓											✓ ^{o)}
Blood sample for anti-drug antibodies	✓									✓					
Blood sample for metabolic profiling															✓ ^{p)}
24-hour urine collection for metabolic profiling															✓ ^{q)}
PD/Exploratory Efficacy Assessments															
Blood sample for biomarkers (optional) ^{g)}	✓									✓					
PROMIS and GAS questionnaires ^{g)}	✓									✓					
EAT-10 Dysphagia questionnaire ^{g)}	✓														
Respiratory function ^{g) r)}	✓			✓						✓					
MyoGrip ^{g) r)}	✓									✓					
MFM32 ^{g) r)}	✓									✓					

AE: adverse event; BP: blood pressure; EAT-10: Eating Assessment Tool; ECG: electrocardiogram; EoT: End of Treatment; FU: follow-up; GAS: Goal Attainment Scaling; IMP: investigational medicinal product; IPF: immature platelet fraction; IV: intravenous; MAD: multiple ascending dose; MFM: Motor Function Measure; PD: pharmacodynamics; PK: pharmacokinetics; PROMIS: Patient Reported Outcomes Measurement Information System; RR: respiratory rate; SAE: serious adverse event.

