- Where possible, the visits in the MAD part will take place on the same day of the week as Day 1 (and of the SAD part, if applicable). A window of ±3 days is allowed for visits as of Week 3, with a minimum of 4 days between 2 subsequent infusions. Assessments of a single visit can be split over 2 consecutive days, if required.
- Replacement subjects starting in the MAD part should sign an ICF for participation in the MAD part, and their eligibility will be assessed (see Trial Schedule for the Screening Period) before the first IMP administration in the MAD part (MAD Week 1 Day 1). If needed (to be discussed with the sponsor), these subjects will have a run-in period before they can start in the MAD part (see Trial Schedule for Run-in Period). A DNA sample (optional) and a muscle biopsy should be taken before the first IMP administration. If needed, replacement subjects in MAD1 and MAD2 may have the second muscle biopsy taken after 6 to 12 weeks of MAD treatment, after discussion with the sponsor.
- All assessments need to be done pre-dose.
- Slow infusion over 1 hour; subjects will be monitored on site by qualified site personnel for a minimum of 1 hour after the infusion for safety. Platelet counts as determined by the local laboratory need to be within normal ranges before IMP administration.

- e) A symptom-directed physical examination (and measurement of body weight at MAD Week 1 Day 1) will be performed.
- f) During an unscheduled visit which will occur between 6 weeks and 7 days prior to the baseline visit for subjects for whom the last visit in the SAD part will be more than 3 months before the baseline visit in the MAD part.
- g) To be performed pre-dose.
- h) Only applicable if a liver ultrasound and/or hepatic elastography was not performed during the screening period.

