6.1.3.4 MAD Extension Part

After completion of the MAD part, subjects will continue on the IMP dose level of their assigned MAD cohort for an additional 12 weeks with weekly IV administrations (MAD Weeks 13-24) (unless the IDMC advises otherwise).

End-of-treatment assessments will be performed after 24 weeks of MAD treatment have been completed, i.e. at the Week 25 visit.

After Week 24, all subjects will remain on treatment with weekly IMP administrations and assessments every 2 weeks until the last MAD3 subject has completed the MAD Week 25 visit. Data collected during this period will be listed and tabulated in the clinical trial report but will not be included in the statistical modeling.

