## **9 INDEPENDENT DATA MONITORING COMMITTEE ANALYSIS**

The purpose of the IDMC is to review study data of the cohorts, before proceeding to the next dose level. Further details about Independent Data Monitoring Committee (IDMC) meetings and deliverables are described in IDMC Charter. IDMC will be reviewing data at least 4 time during the study:

1. Organizational Meeting.
2. First Data Review Meeting
  - When last subject from SAD1 has completed study visit SAD1 W3 (Day 15).
3. Second Data Review Meeting
  - When last subject from SAD2 has completed study visit SAD2 W3 (Day 15)
4. Third Data Review Meeting
  - When at least two subjects in each sub cohort have passed study visit MAD1 W6 and all available SAD3 data available at the time of the meeting (SAD3 dosing is optional for this IDMC meeting)

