#### 5. Fourth Data Review Meeting

- When last subject from MAD1 has completed study visit MAD1 W13 and last subject from MAD2 has completed study visit MAD2 W13

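### The protocol opens MAD2 on 6-week MAD1 data, but the SAP lets the third IDMC review be triggered at visit MAD1 W6, nominally 5 weeks after first dose

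*Protocol*

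**What the plan says.** Protocol section 3.1.1 and the synopsis make the opening of MAD2 conditional on a favourable IDMC review of 2-week SAD3 data, if available, "as well as the 6-week safety and PK data of MAD1 (IDMC3"). SAP section 9 sets the third data review for this point: "When at least two subjects in each sub cohort have passed study visit MAD1 W6".

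The other reviews in SAP section 9 are tied to visits as follows. For IDMC1, where the protocol asks for 2-week data: "When last subject from SAD1 has completed study visit SAD1 W3 (Day 15"). IDMC2 uses the same visit for SAD2. For IDMC4, where the protocol asks for 12-week data, MAD1 must have reached W13 and "last subject from MAD2 has completed study visit MAD2 W13". Protocol section 6.1.3.4 places the end-of-treatment assessments "after 24 weeks of MAD treatment have been completed, i.e. at the Week 25 visit".

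**The concern.** The SAP trigger does not guarantee the data that the protocol requires. IDMC3 is the gate from 1.5 to 4.5 mg/kg weekly in a first-in-human trial, and Protocol section 9.12 lets the IDMC decide separately for the *DNM2* and *MTM1* sub-cohorts. Under the SAP rule a sub-cohort could be reviewed a week short of the required follow-up, with no scheduled MAD examination or ECG after the pre-dose record on Day 1.

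Those two assessments matter here. Vasculitis is an adverse event of special interest, and Protocol section 7.2 says that, without a validated marker, monitoring rests on clinical suspicion, physical examination and organ-specific studies. SAP section 12 lists ECG tables and the physical-examination listing as outputs for IDMC meetings 1 to 4. Six weeks also has a pharmacological meaning in this programme: Protocol section 1.3.1 predicts 90% of steady state after 6 weeks of weekly dosing.

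**Working it through.** **Inputs**
- Weekly MAD dosing from Week 1 to Week 12: Protocol 6.1.3.3.
- Visit window: "A window of ±3 days is allowed for visits as of Week 3" (MAD schedule, footnotes).
- Sentinel stagger: "with an interval of at least 7 days between dose administration of the first and the next subject in a cohort" (Protocol 3.1.1). No stagger is required after that.
- Trigger set: at least two subjects in each of two sub-cohorts (SAP section 9).

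**Step 1: check the visit numbering against the documents.** The nominal day of visit W*k* is 7 × (*k* − 1) + 1, and elapsed weeks are *k* − 1.

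| Visit | Calculated day | Elapsed weeks | What the documents say |
|---|---|---|---|
| SAD W3 | 15 | 2 | Day 15, +2 weeks; used for 2-week data at IDMC1 and IDMC2 |
| SAD W5 | 29 | 4 | Day 29, +4 weeks |
| SAD W7 | 43 | 6 | Day 43, +6 weeks |
| SAD W17 | 113 | 16 | Day 113, +16 weeks |
| MAD W13 | 85 | 12 | used for 12-week data at IDMC4 |
| MAD W25 | 169 | 24 | 24 weeks of MAD treatment completed |

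The rule reproduces every SAD visit day from W2 to W17 and both MAD anchors.

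**Step 2: apply it to IDMC3.**
- W6: 7 × 5 + 1 = Day 36, or 35 days = 5.0 weeks after first dose. With ±3 days it is Day 33–39, or 32–38 days elapsed (4.57–5.43 weeks). No in-window W6 visit reaches 42 days.
- W7: 7 × 6 + 1 = Day 43, or 42 days = 6.0 weeks. With ±3 days it is Day 40–46.
- Doses: five precede the W6 pre-dose assessments, and six have been given by the end of that visit. At W7, six precede the pre-dose assessments.

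**Step 3: what lies between W6 and W7.** The MAD schedule has 15 visit columns (W1 D1, D2, D4; W2 D8, D11; W3 to W12). The rows for physical examination and "Triplicate 12-lead ECG" are ticked in columns 1 (W1 D1, pre-dose) and 10 (W7) only. Plasma PK is sampled around Week 1 and from Week 12, so neither W6 nor W7 adds a PK sample. Anti-drug antibodies are not listed among the IDMC outputs.

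**Step 4: who would have W7 data at the minimum trigger.** The minimum set is 2 × 2 = 4 subjects. If the second subject is dosed exactly 7 days after the sentinel and attends W6 on Day 36, the sentinel is at Day 36 + 7 = 43, which is W7. If that W6 visit falls on Day 33, the sentinel is at Day 40 and its W7 visit could still be 46 − 40 = 6 days away. The other three subjects can all be at W6 together. Scheduled on-treatment MAD examination and ECG are then nominally available for 1 of 4 subjects, and for 0 of 2 in the sub-cohort that does not contain the sentinel. Under a W7 trigger this becomes 4 of 4.

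**The case against.** The strongest reply is that the two texts can both be satisfied. The protocol says what must have been reviewed before MAD2 opens; the SAP says when a meeting may be called. The SAP cannot open a cohort, W6 is a minimum and not a data cut, and SAP section 6.2.14 gives the IDMC cumulative data on all dosed subjects. All of that stands. It limits the harm, but a trigger should secure the data that its gate requires, and this one does not.

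A second reply is that no text ties 6-week MAD1 data to a named visit. Twelve weeks of dosing is described as Weeks 1 to 12, and the SAP uses a different verb for IDMC3 (subjects have passed W6) than for the other meetings (subjects have completed the visit), so the sixth treatment week might be meant. This reading is possible. But the SAP names a study visit, and the other triggers in the same section use visit n+1. At best the wording is ambiguous at a dose-escalation gate.

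Third, the charter governs the detail of IDMC reviews, and the SAP change log says section 9 was updated to match it. The charter is not among the documents, so the W6 visit may come from there. That bears on where the correction is made, not on whether the SAP matches the protocol.

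Fourth, much safety information exists at W6: weekly platelets, laboratory tests, vital signs and adverse events; troponin, complement and urinalysis at W3 and W5; and the SAD examinations and ECGs. A single 4.5 mg/kg dose has been reviewed at IDMC2, and the IDMC may meet at any time. This is accepted.

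Fifth, the 1-of-4 and 0-of-2 counts describe the least that the rule allows, not what happened. That is also right. Finally, SAP section 10 does not mention the difference, but it deals mainly with analyses and reporting, so its silence carries little weight.

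**Conclusion.** The mismatch holds. The SAP permits IDMC3 at nominal Day 36 (Day 33–39), while 6-week data by the documents' own numbering means Day 43 (Day 40–46): one week short, and before the first scheduled on-treatment MAD examination and ECG. The consequence is moderate. The protocol condition still governs the opening of MAD2, so the defect is that a meeting may be called which does not satisfy it, possibly for a whole sub-cohort.

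The conclusion assumes that the visit numbering used for IDMC1, IDMC2, IDMC4 and Week 25 applies to IDMC3 too, and that the unseen charter contains no separate rule requiring W7 data. The subject counts assume the minimum trigger set and no stagger beyond the sentinel. The documents do not show whether IDMC3 was held, or on which visit.

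**What to change.** In SAP section 9, third data review, change the trigger visit from MAD1 W6 to MAD1 W7, and make the same change in the IDMC charter if it repeats the visit. The cost is one word in each document and up to about one week before IDMC3.

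SAP version 3.0 was issued after the trial was terminated, so the edit may have no prospective use. If IDMC3 was held on the W6 trigger, the CSR should instead state which visit was used, how many subjects in each sub-cohort had W7 data at the review, and that this departs from the protocol's 6-week requirement. That costs one sentence.
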